12.2.3. Definition of Pharmacodynamic Efficacy Measures

AFP elevation is an important marker of disease progression in HCC. Hence, a treatment effect can be measured by following the kinetics of AFP reduction during the treatment period. It is estimated that a reduction of 50% over 3 months is a relevant change suggesting a treatment effect.

Less validated is the increase of TGF- β 1 levels in HCC patients. However, there is a body of studies suggesting that levels above 800 ng/mL are correlated with poor clinical outcome. Hence, a reduction in TGF- β 1 levels is another marker of activity of a beneficial treatment effect. Given that LY2157299 is specifically designed to reduce TGF- β -related pathology, a change in the TGF- β 1 kinetics is an important proof-of-concept for the activity of LY2157299.

Finally, E-cadherin is a protein associated with the EMT. Its levels were found to be increased in aggressively growing HCC. Hence, a change in kinetics of its levels may reflect treatment effects.

12.2.4. Patient Disposition

A detailed description of patient disposition will be provided. It will include the following:

- a summary of data on patient discontinuation
- a summary of data on overall qualification status of all patients
- an account of all identified protocol violations

All patients entered in the study will be accounted for in the summary. The number of patients who do not qualify for analysis, who die, or who discontinue before treatment begins will be specified.

12.2.5. Patient Characteristics

Patient characteristics will include a summary of the following:

- patient demographics
- baseline disease characteristics
- preexisting conditions
- historical illness
- prior therapies
- concomitant drugs

Other patient characteristics will be summarized as deemed appropriate.

12.2.6. Concomitant Therapy

Concomitant medications will be listed and may be summarized by World Health Organization (WHO) preferred name.

12.2.7. Treatment Compliance

A summary of treatment compliance will be generated using information from drug accountability records and the patient diary. A patient will be considered compliant with the study-therapy protocol if pill counts indicate the patient took at least 80% of LY2157299 during the preceding cycle of study therapy (refer to Section 9.9).

An attempt may be made to determine how compliance to study treatment relates to observed study-related outcome.

12.2.8. Clinical Efficacy Analyses

Kaplan-Meier analysis will be performed on the observed distribution of TTP (Kaplan and Meier 1958) for each dose in Part A, Part B, Part C, Part D and Part E, with parameter estimates of the TTP median and quartiles being reported. All parameter estimates will be quoted together with their 90% confidence limits. The hazard ratio between the observed TTP distributions of each cohort in Part A will be estimated, recognizing that since 1 dose cohort did not enroll to its full

complement, the precision of the HR will be lower than originally planned. The hazard ratios between the 300 mg/day cohort in Part A and Part B cohort will also be estimated. In addition, the hazard ratio between a subgroup of sorafenib-naïve patients in Parts A and B and patients in Part C may be estimated. The interpretation of any estimate will be considered in light of the size of this subgroup.

Alternative distributions of TTP times, such as exponential Weibull (estimating a shape parameter may also be considered) where median TTP and its 90% CIs will be reported. Individual parameters, such as TTP rate after specific time points (for example, after 12 months on treatment) will be estimated from the TTP distribution.

Secondary efficacy measures include other time-to-event parameters, and these will follow the same analyses as described above.

The overall response rate (ORR) for each cohort in Part A, Part B, Part C, Part D and Part E will be estimated by dividing the total number of confirmed responders by the number of patients who received at least 1 dose of study treatment. The clinical benefit rate will be estimated for each treatment group by dividing the total number of patients experiencing benefit by the number of patients who received at least 1 dose of study treatment. A patient is considered to have received benefit if they achieve a confirmed response, CR or PR, or SD per RECIST v1.1 or mRECIST. Both mean and exact confidence limits will be provided for each group (Cohort 1 and Cohort 2 in Part A, Part B, Part C, Part D and Part E, as well as estimates of differences between 2 cohorts in Part A, between Parts A and B at 300 mg/day, and between sorafenib-naïve patients in Part A and Part B with those in Part C. The interpretation of any estimate in the latter comparison will be considered in light of the size of this subgroup.

Additional exploratory analyses of efficacy endpoints will be performed to assess the effect of important prognostic factors on the outcome, including, but not exclusively, baseline AFP levels (either as a continuous factor and/or categorical factor), etiology, and whether sorafenib-naïve or not. Analyses using subgroup identification methods, such as classification and regression tree (CART) (classification and regression tool) may also be carried out. The only difference between Part A and Part B patients is their baseline AFP levels, and therefore results from Cohort 2 in Part A and Part B will be combined in these analyses. Similar analyses for patients in Parts C, D and E may be carried out.

The original statistical analysis plan (SAP) was finalized prior to the first patient in the study being dosed. The amended SAP was finalized prior to the first patient in Part B being dosed. The amended SAP (version 2) was finalized prior to the first patient in Part C being dosed. The amended SAP (version 3) will be finalized prior to the first patient in Part D being dosed. An amended SAP (version 4) will be finalized prior to the first patient in Part E being dosed.

12.2.9. Pharmacodynamic Efficacy Analyses

Pharmacodynamic (PD) parameters (for example, AFP, E-cadherin, TGF- β 1) will be analyzed using a mixed-effects model with patient as a random effect and dose, time of sample, and baseline values as fixed effects. Two effects of LY2157299 are of interest for changes in AFP

levels: first, whether there is evidence of a reasonably sustained (≥ 2 months) 50% or greater reduction from baseline (as this is considered indicative of clinical benefit) in either dose. Second, whether there is a difference of 20% in the percentage change from baseline between the 2 doses (eg, 50% reduction at 300 mg/day and 30% reduction at 160 mg/day).

Comparisons between subgroups of interest (baseline AFP [as a continuous covariate and subgroups categorized by cutoff values], etiology, and whether sorafenib-naive or not) will be carried out by either including these terms as fixed effects, including interaction terms if needed) in the above model or as separate analyses. The decision will be in part based on whether there is any evidence that the variability of data differ between the different subgroups and the actual number of patients enrolled in each subgroup. A variance-covariance structure will be added to the model as appropriate. Serum concentrations will be log transformed prior to analysis as concentration data are typically log normally distributed, and the comparisons of interest are fold differences between different groups as opposed to absolute differences. In addition to the above 2 analyses, the percentage of patients who have at least 2 cycles of reductions of at least 25% AFP levels will be provided. Percentages of patients for other cutoff values may also be provided. With the early closure of Cohort 1 in Part A and addition of Part B, the above effects of interest will be investigated by providing summary statistics and estimating differences between study Parts A and B for patients on 300 mg/day.

The association between changes in PD parameters and clinical endpoints will be explored to determine their value as predictive biomarkers of drug effect on clinical outcome.

Summary statistics for each parameter will be provided by dose, time, and subgroup of interest. Estimates of fold differences from the model (between doses for each subgroup of interest and also between subgroups of interest within each dose) will be provided together with their 95% CIs. Visual presentation of the results will be provided where meaningful.

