1. If the observed mean percentage reduction from baseline in AFP concentrations in either cohort was more than 50%, enrollment into the dose cohort may continue.
2. If the difference in mean percentage change from baseline in AFP concentrations between the 2 doses is $>20\%$, then the dose with the lowest reduction from baseline may be dropped after taking into consideration the observed results for E-cadherin and other TGF- β related biomarkers.
3. Either dose or both doses will be dropped if there is evidence of cardiotoxicity and/or drug-related CTCAE Grade 3/4 toxicity that is not manageable in any patient.
4. If the number of patients who are free from progression at 3 months in either dose is 21 or less, then the dose level may be discontinued.
 - o This cut-off represents a risk of continuing when the true median TTP is not considered clinically meaningful over no intervention (that is, median TTP = 3 months) is 32% and of deciding not to continue when the true median TTP is considered meaningful (that is, median TTP = 4.5 months) is 11%. (Information for risks of an incorrect decision using other cutoff values will be provided in the SAP.)

Two effects of LY2157299 are of interest for changes in AFP levels – whether there is evidence of a reasonably sustained 50% or greater reduction from baseline (as this is considered indicative of clinical benefit) in either dose and whether there is a difference of 20% in the percentage change from baseline between the 2 doses (for example, 50% reduction at 300 mg/day and 30% reduction at 160 mg/day). With 40 patients enrolled at each dose cohort and an assumed within-patient coefficient of variation of 44% (data on file), there is at least 95% probability that treatment effect of 50% within a dose group will be detected as significant at the 5% significance

level. The more sensitive situation concerns the probability of detecting a difference of 20% in the percentage reduction in pre and postdose concentrations between the 2 dose groups in order to choose a dose at this stage. The power to detect a 20% difference in percentage reduction between the 2 doses is approximately 80%, at the 20% 2-sided significance level.

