ECG chemistry		X							X		X		X	X ^b	X ^b	Cycle 2, 3, 4, and every other cycle (C6, C8,...etc). Perform predose on Day 1 of each cycle in extension period. Can be done at local labs during the extension period
Special chemistry			X		X	X		X	X	X	X	X	X	X		Perform predose on Day 1 of each cycle in extension period. Can be done at local labs during the extension period
Hematology			X		X	X		X	X	X	X	X	X	X		Perform predose on Day 1 of each cycle in extension period. Can be done at local labs during the extension period
Serum chemistry			X		X	X		X	X	X	X	X	X	X		Perform predose on Day 1 of each cycle in extension period. Can be done at local labs during the extension period
Urinalysis		X							X		X			X		Optional during the extension period (including extension period V801)
Urine C-terminal telopeptides of Type 1 collagen		X							X		X					Optional during the extension period

Cycle/Visit ^j	Prestudy			Cycle 1					Cycle 2		Cycle 3, n ^l		Extension Period	Visit 801	Follow-up ^f	Comments
	≤28	≤14	≤7	1 ⁱ	8 ⁱ	14 ⁱ	15	22	1 ⁱ	14 ⁱ , k	1 ⁱ	14 ⁱ , k				
PK sampling ^e				X		X	X	X	X		X					Timed with ECG
Serum markers (AFP, AFP L3, E-cadherin, PIVKA II)		X		X		X			X	X	X	X	AFP only	X		Perform predose on Day 1 of each cycle in extension period. Can be done at local labs during the extension period
Immuno-phenotype				X					X		X			X		Optional during the extension period (including extension period V801)
TGF-β+PF4		X		X		X			X	X	X	X		X		Optional during the extension period (including extension period V801)
MAP panel		X				X				X		X		X		Optional during the extension period (including extension period V801)
Fibrotest		X				X				X		X				
aPTT/PT/ INR		X		X					X		X		X			Perform predose on Day 1 of each cycle in extension period. Can be done at local labs during the extension period
Patient-Reported Outcomes																
FACT-Hep		X							X		X			X		Optional during the extension period (including extension period V801)

Cycle/Visit ^j	Prestudy			Cycle 1					Cycle 2		Cycle 3, n ^l		Extension Period	Visit 801	Follow-up ^f	Comments
	≤28	≤14	≤7	1 ⁱ	8 ⁱ	14 ⁱ	15	22	1 ⁱ	14 ^{i,k}	1 ⁱ	14 ^{i,k}				
Relative Day Within a Cycle																
Translational Research																
Whole blood for PGx		X														
Obtained diagnostic tumor tissue, when available		X														
Optional tumor biopsy	X								X							+/- 3 days after end of treatment with LY2157299

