5.1.3. Pharmacodynamic Efficacy Endpoints

Elevated AFP is a marker of disease progression in HCC patients. Hence, a treatment effect can be measured by following the kinetics of AFP reduction during the treatment period and a sustained reduction of 50% over 3 months is a relevant change suggesting a treatment effect.

Other AFP response criteria will be studied including the following definition : AFP response is >20% decrease in AFP from baseline (samples collected closest to first dose) during 8 weeks of treatment.

Elevated TGF- β 1 (possibly adjusted for PF4 level), though less validated, correlated with poor clinical outcome in HCC patients. Hence, a reduction in TGF- β 1 levels is another marker of activity of a beneficial treatment effect.

The protein, E-cadherin, is associated with EMT and elevated levels of this marker is found in aggressively growing HCC. Hence, a change in kinetics of its level may reflect treatment effect.

Additional PD endpoints (for example, Fibrotest, T-cells counts, AFP L3, PIVKII) may be considered for analysis.

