Baseline	
For change from baseline analysis, baseline value is defined as the last reported measure on or before the first dose date. For change from baseline within a cycle, the measure prior to the first dose if that cycle is baseline.

Entered	Patients who have signed the informed consent document directly.
Randomized	Patients who have been assigned to study treatment and have not received any study treatment (LY2157299).
Screen failures	Patients who have signed informed consent, do not meet eligibility criteria and are not randomized.
Enrolled, Patients on therapy	Patients who have been assigned to study treatment and have received at least 1 dose of study treatment (LY2157299).

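### The biomarker model does not use the screening value of the serum markers; entering both predose values as covariates would narrow between-group intervals modestly

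*Protocol*

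**What the plan says.** - **Sampling.** Protocol Attachment 1 has a row for "Serum markers (AFP, AFP L3, E-cadherin, PIVKA II") and a row for TGF-β with PF4. Both are marked in the prestudy column (14 days or fewer) and on Cycle 1 Day 1, and a footnote makes Day 1 procedures predose. Parts C, D and E carry the same two marks. Attachment 2 sends all these markers to the sponsor-designated laboratory.
- **Model.** Protocol 12.2.9 states that the parameters "will be analyzed using a mixed-effects model with patient as a random effect and dose, time of sample, and baseline values as fixed effects", on the log scale. SAP 5.3.8.2 repeats this.
- **Baseline.** In SAP 5.3.3 the "baseline value is defined as the last reported measure on or before the first dose date". For one AFP response criterion, SAP 5.1.3 measures the decrease "from baseline (samples collected closest to first dose"). Neither document gives the screening value any use once a Day 1 value exists.
- **Noise.** Protocol 12.2.14 gives "an assumed within-patient coefficient of variation of 44% (data on file").
- **Status.** The serum-marker effect stands beside TTP in the primary objective (6.1). Part A enrolled 37 patients at 160 mg/day and 72 at 300 mg/day (12.1).

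**The concern.** A single predose measurement carries assay and day-to-day noise into the baseline term. Extra post-dose visits average down the post-dose noise but leave the baseline noise untouched. A second predose measurement of the same markers reduces it, and the trial already collects one. One Part A dose cohort closed early, and both documents promise dose and subgroup ratios with 95% intervals, so unused precision has some value. No formal efficacy test is planned (12.1), so what is lost is interval width, not a failed test.

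**Working it through.** **Log-scale SD.** s = √ln(1 + 0.44²) = 0.4207, so s² = 0.177.

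**The plan's own figure.** Protocol 12.2.14 says "The power to detect a 20% difference in percentage reduction between the 2 doses is approximately 80%, at the 20% 2-sided significance level", with 40 patients per dose. Taking 0.20 as a log difference and 0.4207 as the SD of the change: 0.20 / (0.4207 × √(2/40)) = 2.126; 2.126 − 1.282 = 0.844; power 80.1%. The figure reproduces, but only on that reading. If 44% is the CV of one sample and the effect is the example of "50% reduction at 300 mg/day and 30% reduction at 160 mg/day", the log difference is ln(0.7/0.5) = 0.336, the SD of change is 0.4207√2 = 0.595, and power is 89.4%.

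**Residual variance per patient with baseline as covariate.** V = b² + h² + s²/k − b⁴/(b² + e), where:
- b = between-patient log SD (not in the documents; assumed 0.3 to 2.0)
- h = SD of true response between patients (not in the documents; 0 unless stated)
- k = post-dose samples averaged
- e = s² with one predose value, s²(1 + r)/2 with two whose errors correlate at r

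With equal error variances the best weights on two predose values are equal, so the same formula describes both entered as covariates, apart from one degree of freedom.

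**One visit (k = 1, h = 0, r = 0).**

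| b | V, one value | V, two values | SE ratio | SE lower by |
|---|---|---|---|---|
| 0.3 | 0.237 | 0.222 | 0.968 | 3% |
| 0.5 | 0.281 | 0.242 | 0.929 | 7% |
| 1.0 | 0.327 | 0.258 | 0.888 | 11% |
| 2.0 | 0.346 | 0.264 | 0.872 | 13% |

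The ceiling at one visit is 1 − √0.75 = 13.4%, whatever the CV. Near that ceiling, with 37 v 72 patients, the SE of the log ratio goes from 0.4207 × √2 × √(1/37 + 1/72) = 0.120 to 0.4207 × √1.5 × √(1/37 + 1/72) = 0.104. The 95% margin goes from a factor of 1.27 to 1.23.

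**Correlated predose errors (k = 1).** At r = 0.5 the gain is 5% to 6% for b of 1.0 or more; at r = 0.8 it is about 2%. It is smaller still for smaller b.

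**Six-visit average (k = 6, b = 2.0, r = 0).**
- h = 0: V 0.199 to 0.116, SE 24% lower
- h = 0.5: V 0.449 to 0.366, SE 10% lower
- h = 1.0: V 1.199 to 1.116, SE 4% lower

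**Averaging as the reference for within-dose change.** If a marker rises before treatment, an average reaching back g days lowers the log baseline by ½ × g × ln2 / T, where T is the doubling time. Take g = 14, 40 patients and one post-dose sample. The mean squared error with the last value alone is 2s²/40 = 0.0088. With the average it is 1.5s²/40 + bias²:
- T = 60 days (assumed): bias 0.081, baseline about 8% low, MSE 0.0132 (worse)
- T = 180 days (assumed): bias 0.027, MSE 0.0074 (better)

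So averaging trades variance against bias, and the documents do not settle which prevails.

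**The case against.** The strongest reply is that the last predose value is a standard, prespecified baseline closest to treatment start, and that the gain is small. Several parts of this stand.

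- **The comparison is not cleanly randomized.** After Cohort 1 closed, later Part A patients were all assigned 300 mg/day, and SAP 5.3.6.1 plans a check on whether their prognosis was worse. Pre-treatment drift need not cancel between doses. Protocol 12.2.9 now directs the AFP questions to Part A v Part B at 300 mg/day.
- **Selection.** Parts A and B are split on local screening AFP, in opposite directions. An average containing a screening-time value could bring opposite regression to the mean into A v B. This counts against averaging. Entering both values as separate covariates conditions on the screening measurement and avoids most of this, though not necessarily all.
- **The 44% is narrow.** It is given for AFP only, for an interim analysis that was not carried out.
- **The rule is partly inferred.** SAP 5.3.3 words it for change-from-baseline analyses, and the protocol's baseline period (Section 10) runs from screening to first treatment. If the rule does not govern the covariate, the covariate is undefined, which also needs wording.
- **Timing.** Parts A and B are complete and reported (5.1.5.2), so a new primary baseline there would be post hoc.

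A reader might infer a much larger gain: 24% lower SE, or 0.199/0.116 = 1.71 times the patients, for six visits. That needs a wide between-patient spread, no variation in true response and independent predose errors, none of which the documents give. Nor is a six-visit average a planned estimate: SAP 5.3.8.2 reports geometric means by dose and time, and the sixth scheduled post-dose sample (Cycle 4 Day 1, about 12 weeks) falls at the Part A median TTP of 11.9 weeks.

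**Conclusion.** The point holds as a modest, nearly free improvement to the between-group model estimates, not as an error that undermines the biomarker objective. The screening value is collected and has no stated use in the model. Including it lowers the SE by about 3% to 13% at one visit for between-patient log SD 0.3 to 2.0 with independent predose errors. The reduction is about 4% to 10% for a six-visit average with response SD 1.0 to 0.5 (between-patient SD 2.0), and about 2% at one visit if the predose errors correlate at 0.8. Between-patient SD, response SD and error correlation are all assumptions.

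A reader might also infer that the mean of the two samples should become the baseline everywhere. The documents do not support that: the first AFP question in 12.2.9 is a within-dose reduction, where drift has no comparator in which to cancel, and Parts A and B are selected on screening AFP. The supplied SAP is aligned with Amendment (c); the later versions named in Protocol 12.2.8 were not available, so the baseline rule for Parts D and E is unconfirmed.

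**What to change.** In Protocol 12.2.9 and SAP 5.3.8.2, state that between-group estimates from the biomarker model include both log-transformed central-laboratory predose values, screening and Cycle 1 Day 1, as separate covariates, and that the available value is used if one is missing. Keep the last predose value as the reference for within-dose fold change, percent change, AFP response and listings, and say why the average is not used there. For Parts A and B, report the two-covariate model as a labelled sensitivity analysis beside the specified one.

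The cost is wording, one more model term and about one degree of freedom. No patients, visits or samples are added.

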12.2.10. Pharmacokinetic/Pharmacodynamic Analyses

The plasma concentration versus time data together with information on dosing and patient characteristics will be pooled and analyzed using a population PK analysis approach. Nonlinear mixed-effect modeling (NONMEM) will be used for the estimation of the population PK parameters of LY2157299.

All patients who have completed at least 2 days of sampling will be included in the PK analysis. LY2157299 PK will be modeled using NONMEM. These population parameters describe the average dose-concentration relationship in the target population, the influence of fixed effects (such as weight or age) on a PK parameter of interest, the interindividual variation in the PK parameter, and the residual variation in the observed concentration.

For the purposes of the JBAK study report, plasma-concentration data will be illustrated graphically and summarized descriptively. If data are sufficient, then data from patients in this study will be modeled using the population approach for characterizing LY2157299 PK. In addition, if appropriate, data from patients in this study will be combined in a PK database with data from Study JBAH and other completed studies, for population PK analysis. In Part C, Cycle 1 assessment on possible sorafenib exposure change during monotherapy and combination

will be made. In Part D, Cycle 1 and 2 assessment of the possible LY2157299 exposure and/or ramucirumab change when administered in combination will be evaluated. In Part E, Cycle 1 LY2157299 PK profile of patients dosed for 21 days on treatment and 7 days off treatment will be characterized.

Exploratory PK/PD analyses will be conducted to identify the exposure-response (biomarker) relationship in this study. The PK and PK/PD analyses may be reported as separate stand-alone reports for this study. Additional analyses such as exposure-response using TTP and/or other appropriate clinical endpoints may be explored, if data warrant.

The version of any software used for the analysis will be documented, and the program will meet Lilly requirements of software validation. It is possible that other validated equivalent PK software programs may be utilized if appropriate, warranted, and approved by global PK management.

